### 6.2.3 Multiplicity/Multiple Testing

The primary analysis compares the combined two highest dalcetrapib dose groups against placebo as well as each treatment group individually. No adjustments will be made for multiple testing.

## 6.3 Study Subjects

### 6.3.1 Subject Disposition

Number of subjects randomized, number of subjects who took at least one dose of study medication, number of subjects completing the study and reasons for not completing the study will be summarized by randomized treatment group, for all randomized subjects as well as for the ITT population.

A listing of subject disposition will be presented (Section 7, Listing 1).

Subject disposition will also be presented with a flow chart reporting the following information: subjects who signed informed consent, subjects who are screen failures, subjects randomized (excluding screening failures that were randomized), subjects who took at least one dose of study medication, subjects completing the study and reasons for study discontinuation (Section 7, Figure 1).

Which visits were done will also be summarized overall and by treatment group, for the ITT population.

### 6.3.2 Protocol Deviations

Protocol deviations will be summarized overall and by treatment group for the ITT population.

A listing will also be provided (Section 7, Listing 3).

### 6.3.3 Datasets Analyzed

The number of subjects in the ITT population, PP population and Safety population will be summarized overall and by treatment group.

A listing of datasets analyzed will be presented and will include subject ID, randomization group, ITT population (Yes/No), reason for exclusion from the ITT population, PP population, reason for exclusion from the PP population, Safety population (Yes/No) and reason for exclusion from the Safety population (Section 7, Listing 2).

### 6.3.4 Demographic and Baseline Characteristics

Demographic data such as age, sex, ethnicity, race and smoker will be summarized overall and by treatment group for the ITT population.

In case the date of birth is incomplete [in the eCRF Demographics], the following imputation will be done:

- the partial date will be replaced by the fifteenth day of the month if month and year are known;
- the partial date will be replaced by the first day of July if only the year is known.

A listing of demographic data will be provided (Section 7, Listing 4).

Medical and surgical history such as diabetes, hypertension, prior cardiovascular disease, respiratory disease, renal disease and liver disease will also be summarized overall and by treatment group for the ITT population.

Delays since first symptoms of COVID-19 will be summarized overall and by treatment group, for the ITT population. The number of days between the date of first symptom of COVID-19 and the following dates will be presented in this table: date of positive diagnosis for COVID-19, date of randomization and date of first dose of study medication. In addition, the number of days between the date of positive diagnosis of COVID-19 and the date of randomization will be presented, as well as how the diagnosis of COVID-19 was established.

Delays will be calculated as:

- Date of positive diagnosis for COVID-19 - Date of first COVID-19 symptoms
- Date of randomization - Date of first COVID-19 symptoms
- First treatment start date - Date of first COVID-19 symptoms
- Date of randomization - Date of positive diagnosis for COVID-19

### 6.3.5 Treatment Compliance

Compliance will be assessed if subject took all the pills at each study visit and will be summarized using frequencies and percentages, by treatment group, for the subjects of the ITT population. If subject did not take all the pills, then the number of missed pills will be reported as number of patients (n), mean, standard deviation, median, Q1, Q3, minimum, and maximum.

### 6.3.6 Prior and Concomitant Medications

Prior and concomitant medications will be coded with respect to indication and generic name using the WHO drug dictionary (version MAR2021).

Frequency of use of medications at randomization will be presented for the subjects of the ITT population by therapeutic class and preferred term, overall and for each treatment group.

A medication will be flagged as being ongoing at the time of randomization if:

- Medication start date < randomization date
- AND
- (Medication end date  $\geq$  randomization date OR Medication is ongoing)

In case of missing or incomplete medication start / end dates, the following rules will be applied:

- If 1) the medication start date is completely missing, or 2) only the year is specified, it is the same as the randomization year and randomization did not occur the first day of the year or 3) only the month/year are specified, they are the same as the randomization month/year, then the medication will be assumed to have started before randomization.
- If 1) the medication end date is completely missing, or 2) only the year is specified and it is the same as the randomization year or 3) only the month/year are specified and they are the same as the randomization month/year, then the medication will be assumed to have ended after randomization.
- Otherwise, partial medication start / end dates (month/year or year only) will be compared to the randomization date and the medication will be classified accordingly.

Frequency of use of prior and concomitant medications will also be presented for the subjects of the ITT population by therapeutic class and preferred term, overall and for each treatment group.

A listing of concomitant medication(s) taken by the subject will be provided (Section 7, Listing 5).

#### **6.4 Efficacy Analysis**

The analysis of treatment efficacy will be based on the Intent-to-Treat Population. The PP population will be used for sensitivity analysis. This section is a summary of the planned efficacy analyses of the most important efficacy endpoints including primary and key secondary efficacy endpoints.

##### **6.4.1 Primary Analysis**

The primary endpoint is time to sustained clinical resolution of symptoms (excluding cough, sense of smell and taste) as determined by symptom score. Sustained clinical resolution of symptoms (excluding cough, sense of smell and taste) is defined in Section 4.1. Time to sustained clinical resolution will be calculated as date of resolution – date of randomization + 1. Subjects who did not resolve will be censored at the last time point where they were not resolved [see Section 9 Appendix 1]. The number and percentage of patients whose symptoms resolved will be presented, and to summarize the time to resolution, censored subjects will be imputed with a time to resolution of 29 days and simple medians with 80% confidence intervals will be provided.

The differences in time to sustained clinical resolution of symptoms (excluding cough, sense of smell and taste) between the treatment groups will be evaluated using 2-sided log-rank tests. The combined two highest treatment groups will be compared to placebo in addition to the comparison of individual doses.

The cumulative incidence curve for sustained clinical resolution (excluding cough, sense of smell and taste) will also be presented using 1 – Kaplan-Meier estimates(Section 7, Figure 2). Should there be several deaths, the cumulative incidence curve will be presented under a competing risk model.

A listing with the score of each symptom at each time point will be provided (Section 7, Listing 7).

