### 3. INVESTIGATION PLAN

#### 3.1. Overall Study Design and Plan Description

This is a randomized, double-blind, multicenter, Phase 2a proof-of-concept study in outpatients with confirmed, mild to moderate, symptomatic COVID-19. Dalcetrapib inactivates the 3CLMpro enzyme of Corona virus and therefore stops the viral replication and transcription in cells. It is being planned to use for treatment in patients with COVID-19.

Up to 60 sites in the United States and Canada, and other countries as appropriate based on the pandemic situation, are planned to enroll patients.

Total duration of study participation is up to 32 days. The screening period is planned to occur between 48 to 24 hours prior to dosing. Randomization will occur during the Screening/Baseline visit in order for treatment to be dispensed in time for start of first dose on Day 1. Patients will either receive dalcetrapib 900, 1800, or 3600 mg or placebo for 10 days and be followed for 18 days of follow-up. The study design is summarized in [Figure 2](#).

It is anticipated that 208 patients will be randomized in one of the dalcetrapib treatment arms or placebo (52 patients to each of 900 mg, 1800 mg, 3600 mg and placebo) for 10 days. Patients will be randomized and receive first dose of study drug within 72 hours of receiving a positive PCR or Point-of-care test for SARS-CoV-2. Patients need to have at least two of the 14 common COVID-19-related symptoms described in the inclusion criteria rated as mild or moderate, as evaluated by ePRO assessment. Symptoms will be assessed at each study visit daily for the first 10 days, then at Day 14 and Day 28, and as clinically indicated. Symptoms will be evaluated as absent, mild, moderate, or severe depending on their impact on activity of daily living.

[figure not shown]
SARS-CoV-2 viral loads will be obtained by both saliva (Oragene) collection and mid-turbinate nasal swab self-collected under supervision of healthcare professional (virtual or home visit) at Screening/Baseline, Day 1, Day 3, Day 5, Day 7, Day 10, and Day 28. Patients who require hospitalization after initiation of study treatment will be followed for vital status through Day 28.

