##### **8.4.1.1. Time to Sustained Clinical Resolution**

The primary endpoint is time to sustained clinical resolution as determined by symptom score. Sustained clinical resolution is defined in Section 7.1.1. The primary analysis of this endpoint will be performed on the ITT population. Time to sustained clinical resolution will be summarized by treatment group using Kaplan-Meier methods. Median and associated 95% CI, 25-75 percentiles, and minimum and maximum values will be presented. The number and percentage of patients whose symptoms resolved, and patients censored will be presented.

The differences in time to sustained clinical resolution between the treatment groups will be evaluated using a 2-sided log-rank test, stratified for baseline symptom severity (presence vs absence of moderate or severe symptoms) and by age ( $\leq 65$  years vs  $> 65$  years). The combined two highest treatment groups will be compared to placebo in addition to the comparison of individual doses.

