#### 6.2 Statistical Considerations

Continuous variables will be summarized by the standard descriptive statistics: number of patients (n), mean, standard deviation, median, Q1, Q3, minimum, and maximum, along with confidence interval (CI) for outcome measures when appropriate. Frequency of patient or events and percentages will be summarized for categorical variables, again with CI when appropriate. Time to event variables will be summarized using Kaplan-Meier methods.

All statistical tests will be conducted at a two-sided 0.20 significance level.

Statistical analyses will be performed using SAS Version 9.4 or higher.

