## 9 APPENDICES

### APPENDIX 1

Algorithm used to classify sustained clinical resolution:

For each subject, all ePRO records will be sorted by the date/time. For each assessment, we characterize the record as clinically resolved (i.e., score of 0 for taste and smell and all other symptoms, a score of 0 or 1) or not.

From Day1 to Day10 (or last ePRO assessment before Day14)

- a) If resolved at Day 10 (or last ePRO assessment), identify first date when resolution occurred with no relapse. This is the tentative date of resolution to be confirmed at Day 14 and Day 28.
- b) If not resolved at Day 10 (or last ePRO assessment), re-assess at Day 14.

At Day14:

- c) If resolved for the first time at Day 14 (i.e. was not resolved at Day 10 or before), use date of Day 14 as the tentative date of resolution to be confirmed at Day 28.
- d) If still resolved at Day 14 (i.e. was already resolved at Day10 or before), use date of resolution identified in step a). This is the tentative date of resolution to be confirmed at Day 28.
- e) If not resolved at Day 14, re-assess at Day28.

At Day28:

- f) If resolved for the first time at Day 28 (i.e., was not resolved at Day 14), subject will be classified as resolved within 28 days and date of resolution will be the date of Day 28.
- g) If still resolved at Day 28 (i.e. was already resolved at Day 14), subject will be classified as resolved within 28 days and date of resolution will be the date of resolution identified in step c) or d).
- h) If not resolved at Day 28, subject will be classified as not resolved within 28 days and the date of censoring will be the date of Day 28.

It should also be noted that subjects who do not have an assessment at Day 28 will be classified as non-resolved REGARDLESS if symptoms were resolved up to their last assessment. Date of censoring will be the date of study discontinuation.

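### SAP 6.4.1 reports simple medians with every censored patient set to 29 days, which conflicts with the plan's Kaplan-Meier summaries and is biased upward by dropout

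*SAP*

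**What the plan says.** SAP 6.2 sets the general rule: "Time to event variables will be summarized using Kaplan-Meier methods". Protocol 8.4.1.1 says the same of the primary endpoint: "Time to sustained clinical resolution will be summarized by treatment group using Kaplan-Meier methods", with medians, 95% CIs and quartiles.

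SAP 6.4.1 departs from this for the numerical summary: "censored subjects will be imputed with a time to resolution of 29 days and simple medians with 80% confidence intervals will be provided". The treatment comparison in the same section is a two-sided log-rank test, and the figure is a 1 – Kaplan-Meier curve. Neither uses the value 29. Sections 6.4.2.3 and 6.4.3.1 to 6.4.3.3 apply the 6.4.1 methods to sustained resolution with all symptoms, to viral clearance and to both complete-resolution endpoints.

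SAP Appendix 1 decides who is censored for the symptom endpoints. Its closing remark reads: "subjects who do not have an assessment at Day 28 will be classified as non-resolved REGARDLESS if symptoms were resolved up to their last assessment". For these patients it then fixes when they are censored: "Date of censoring will be the date of study discontinuation". SAP 6.4.4 has a sensitivity analysis, for the primary endpoint only, that carries the last observation forward to a missing Day 28 in patients who are alive.

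**The concern.** Three things look wrong.

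- **Internal conflict.** The general rule in 6.2 and the specific rule in 6.4.1 disagree. Within 6.4.1, the same dropout is censored at discontinuation for the test and curve but is a non-resolver at 29 days for the median. The median in the table need not be the one a reader takes off the curve.
- **Bias.** Each dropout is moved to the far end of the distribution, so the median rises with dropout. Unequal dropout between arms produces a difference in medians without any drug effect.
- **The value 29.** It makes the median finite even when fewer than half of an arm resolve. It is also not reliably later than every resolver's time.

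The trial is meant to inform the decision on Phase 3 and the choice of dose. The arm medians are likely to be read as the size of the effect.

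**Working it through.** The documents give no derivation for the 29 days, so there is no planned figure to reproduce. The checks below start from the stated rules.

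**1. Is 29 later than every resolver's time?**

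Inputs:
- Formula (SAP 6.4.1): "Time to sustained clinical resolution will be calculated as date of resolution – date of randomization + 1".
- A first-time resolver at Day 28 (SAP Appendix 1): "subject will be classified as resolved within 28 days and date of resolution will be the date of Day 28".
- Day 28 window (SAP Appendix 2): 25 to 29 days after first dose, nominally 27.
- Lag from randomization to first dose (Protocol 3.1): "The screening period is planned to occur between 48 to 24 hours prior to dosing. Randomization will occur during the Screening/Baseline visit", so about 1 or 2 days.

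Time = (visit − first dose) + lag + 1:

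| Days from first dose | 25 | 26 | 27 | 28 | 29 |
|---|---|---|---|---|---|
| Lag 1 day | 27 | 28 | 29 | 30 | 31 |
| Lag 2 days | 28 | 29 | 30 | 31 | 32 |

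Of the 10 combinations, 5 exceed 29, 2 equal it and 3 fall below. SAP 4.1, however, treats anyone who has not resolved 28 days after randomization as not resolved. With the +1 in the formula this caps a resolver's time at 28 + 1 = 29. The times of 30 to 32 arise only because Appendix 1 accepts any visit in the Day 28 window.

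**2. How far does dropout move the median?**

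Assumptions, none given in the documents: exponential resolution times with true median 8 days, a fraction d dropping out independently of outcome, uniformly over Days 1 to 14. Under Appendix 1 every dropout is non-resolved, so the simple median t solves (1 − d)F(t) = 0.5 with F(t) = 1 − 2^(−t/8). Hence

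t = −8 × log2(1 − 0.5/(1 − d)).

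For d = 0.05: 0.5/0.95 = 0.526, 1 − 0.526 = 0.474, and t = 8.6. The Kaplan-Meier column is simulated with Appendix 1 censoring unchanged.

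| Dropout | Simple median, censored = 29 | Kaplan-Meier median |
|---|---|---|
| 5% | 8.6 | 8.5 |
| 10% | 9.4 | 8.9 |
| 15% | 10.2 | 9.5 |
| 20% | 11.3 | 10.0 |

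With 15% dropout in one arm and 5% in the other, and no drug effect, the false difference is 10.2 − 8.6 = 1.6 days for the simple median and 9.5 − 8.5 = 1.0 day for Kaplan-Meier.

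The Kaplan-Meier median also exceeds 8, because Appendix 1 removes the resolution of dropouts who had already recovered. At 20% dropout the excess is 11.3 − 8 = 3.3 days for the simple median and 10.0 − 8 = 2.0 days for Kaplan-Meier, so more than half of it remains. If resolution before dropout were kept, the simple medians would be 8.1 to 8.6 and the false difference about 0.3 day.

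**3. What is shown when the median is not reached?**

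Suppose 45% of an arm resolve and nobody drops out. The proportion unresolved at Day 28 is 1 − 0.45 = 0.55, so there is no median, yet the simple rule gives 29. Kaplan-Meier alone does not fully cure this. In a simulation on the SAP visit grid, with Day 28 visits spread over the window, it returned 31 days, because the last few patients at risk drive the curve below one half. With one common Day 28 analysis time the curve would stop at 0.55 and the entry would be *not reached*.

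**The case against.** The strongest defence is that this is a disclosed descriptive convention. The p-value comes from the log-rank test, which never uses 29. The Kaplan-Meier curve for the primary endpoint is shown beside the medians. The SAP states that it supersedes the protocol, and a specific rule in 6.4.1 can be read as overriding the general one in 6.2. Counting non-completers as failures in a 28-day summary is a recognised choice, and the LOCF analysis in 6.4.4 addresses dropouts who had recovered.

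Much of this stands. It limits the harm to the medians and their CIs, and it disposes of the conflict with the protocol. It does not explain why the same patients are failures in the median and censored in the test, and 6.4.4 covers only the primary endpoint.

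A reader might also infer more than the documents support:

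- *That non-resolvers always get a shorter time than Day 28 resolvers.* This happens in 5 of the 10 combinations above, and in none if the SAP 4.1 limit is enforced. It changes a median only when the median falls among the Day 28 times, so not when more than half of the ITT patients are classified as resolved by Day 14.
- *That viral clearance has the same inversion.* Clearance needs two consecutive negative tests and is dated at the first. A first negative at the scheduled Day 28 sample has no later scheduled sample to confirm it, so the latest scheduled clearance date is Day 10.
- *That dropping the 29-day value removes the dropout bias.* It does not, because Appendix 1 causes much of it.

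**Conclusion.** The point holds as a defect in the reported medians and 80% CIs of the endpoints that use the 6.4.1 methods. The simple median conflicts with SAP 6.2, treats dropouts differently from the test and curve it accompanies, rises with dropout, and cannot show that a median was not reached. The log-rank inference is untouched.

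Under the stated assumptions, moving to Kaplan-Meier reduces the median by about 0.1 day at 5% dropout and 1.3 days at 20%, and cuts the false 15% versus 5% difference from 1.6 to about 1.0 day. These sizes depend on the assumed 8-day median, exponential shape and dropout pattern. A flatter resolution curve can give a larger gap: in the visit-grid simulation with 80% resolving by Day 28 and 10% dropout uniform over follow-up, the simple median was 27 days and the Kaplan-Meier median 17, against 16 with no dropout. At 20% dropout both were 28.

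That 29 is not a dependable worst value is a secondary matter. It follows from the mismatch between SAP 4.1 and Appendix 1.

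**What to change.** 1. In SAP 6.4.1, replace the 29-day imputation and simple median with Kaplan-Meier medians and quartiles with 80% CIs by arm, printing *not reached* where that applies. State that this covers 6.4.2.3 and 6.4.3.1 to 6.4.3.3.
2. Keep patients who died in the risk set as unresolved through Day 28, as 6.2.2.2 implies, so that death is not treated as ordinary censoring.
3. Reconcile the limit of 28 days after randomization in SAP 4.1 with the Day 28 window counted from first dose in the appendices, and state the analysis time given to Day 28 visits. Without this, visit spread can still produce a spurious late median.
4. Report the same Kaplan-Meier medians for the LOCF analysis in 6.4.4, so that the effect of the Appendix 1 dropout rule is visible.

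The cost is SAP text and table shells; the Kaplan-Meier estimates for the primary endpoint are already needed for the cumulative incidence figure. The remaining drawback is that the main Kaplan-Meier medians still inherit the Appendix 1 censoring of dropouts who had already resolved, which is why item 4 belongs with item 1.

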### **5.3. Method of Treatment Assignment**

All patients will be centrally randomized using an Interactive Voice/Web Response System (IVRS/IWRS). Before the study is initiated, the telephone number and call-in directions for the IVRS and/or the log-in information and directions for the IWRS will be provided to each site.

The study will be stratified by presence or absence of moderate or severe symptoms and by age ( $\leq 65$  years vs  $> 65$  years).

Patients who confirmed eligible at the screening will be assigned a patient identifier before having study treatment dispensed. The patient identifier will consist of the country number, site number, and patient number. The country number will comprise the first 2 digits, the site number will comprise the next 3 digits, and the patient number will comprise the final 3 digits, e.g., 01002003 is Country 1, Site 2, Patient 3.

Study treatment will be dispensed to patients at the Screening/Baseline visit (see Schedule of Assessments, [Appendix 4](#)).

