## 1 INTRODUCTION

The purpose of this statistical analysis plan (SAP) is to present the statistical methodology that will be used for the final analysis of DalCor Pharmaceuticals DAL-401. This plan also provides a description of the tables, figures and listings that will be included in the final statistical report. It is based on the protocol dated 22-OCT-2020 and on the annotated case report form (CRF) version 1.0. In case of differences in terms of descriptions or explanations between the SAP and the clinical protocol, the SAP will supersede the protocol. Any deviation to this SAP would be reported in the statistical report.

Since the protocol was developed and discussed with the regulatory authorities, a greater understanding of COVID-19 and clinical trials in COVID-19 has emerged. New variants have also been observed and their clinical course needs to be taken into consideration. Based on this emerging knowledge, a higher emphasis will be placed on viral load analyses when interpreting the data and deciding on POC in this study. Less emphasis will therefore be placed on the current primary endpoint of Patient Reported Outcomes and endpoints that look at changes in symptoms of COVID-19. Certain symptoms such as loss of taste and loss of smell as well as cough are chronic symptoms which may not resolve over the course of a 28-day study. In view of this the endpoints evaluating symptoms will not include taste, smell or cough in some analyses.

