### **4 EFFICACY ENDPOINTS**

#### **4.1 Primary Efficacy Endpoint**

The primary efficacy endpoint is:

- Time to sustained clinical resolution of symptoms (excluding cough, sense of smell and taste)

Sustained clinical resolution is defined as occurring when no key COVID-19 related symptom (excluding cough, sense of smell and taste) has a score higher than 1 over a 72-hour period (as documented using an electronic patient-reported outcome [ePRO] instrument or in the eCRF). The time to resolution will be taken as the time from randomization until the first day of the last 72-hour period where the patient meets the definition of resolution within 28 days. Patients who do not meet the definition of resolution 28 days after randomization will be considered not resolved.

The classification of sustained clinical resolution of symptoms (excluding cough, sense of smell and taste) follows similar steps as the algorithm presented in Appendix 1.

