#### 6.4.2.3 Time to Sustained Clinical Resolution

Sustained clinical resolution is defined in Section 4.2.

Same statistical methods as those described in section 6.4.1 will be used to analyze the time to sustained clinical resolution.

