### 6.4.3 Other Secondary Analysis

#### **6.4.3.1 Time to Viral Clearance Based on PCR Test for SARS-CoV-2**

Each subject will be tested to determine if the subject has COVID-19 by obtaining a PCR or rapid antigen test as it confirms the presence of SARS-CoV-2. A subject will be considered to no longer have COVID-19 if two consecutive PCRs do not detect SARS-CoV-2. Time to viral clearance using PCR test for SARS-CoV-2, as assessed using the saliva and using the nasal swab, will be calculated as date of the first negative PCR test for SARS-CoV-2 – date of randomization + 1. Subjects who did not obtain two consecutive negative PCRs will be censored at the date of study completion.

Same statistical methods as those described in section 6.4.1 will be used to analyze the time to viral clearance.

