#### 6.4.4 Sensitivity Analysis

As a sensitivity analysis, the primary analysis described in section 6.4.1 will be repeated on the PP population.

As an additional sensitivity analysis, the primary endpoint will be derived using the algorithm of Appendix 1, but prior to applying the algorithm, the last observation carried forward will be used in alive patients with no assessment at Day 28. In other words, in alive patients, the missing assessment at Day 28 will be imputed as the last available assessment.

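### The SAP drops the randomisation strata from the primary log-rank test without explanation, which costs power if baseline severity is prognostic

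*SAP*

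**What the plan says.** Protocol 5.3 sets the randomisation factors: "The study will be stratified by presence or absence of moderate or severe symptoms and by age", with age cut at 65. Protocol 8.4.1.1 makes the primary test a two-sided log-rank test "stratified for baseline symptom severity (presence vs absence of moderate or severe symptoms) and by age". Protocol 8.3 makes the same two factors the default strata for regression models.

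SAP section 1 states that where the documents differ, "the SAP will supersede the protocol". SAP 6.4.1 then says that differences "between the treatment groups will be evaluated using 2-sided log-rank tests", for the two highest doses combined and for each dose against placebo. No strata are named.

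The same test is reused elsewhere. SAP 6.4.2.3 says: "Same statistical methods as those described in section 6.4.1 will be used to analyze the time to sustained clinical resolution". SAP 6.4.3.1 says: "Same statistical methods as those described in section 6.4.1 will be used to analyze the time to viral clearance". SAP 6.4.3.2 and 6.4.3.3 do the same for the two complete-resolution endpoints.

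SAP 6.4.4 has two sensitivity analyses. In one, "the primary analysis described in section 6.4.1 will be repeated on the PP population". The other carries the last observation forward to Day 28. Neither uses the strata.

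**The concern.** When arms are balanced within strata that predict outcome, the between-stratum part of the outcome variation no longer contributes to the difference between arms. An unstratified log-rank test still counts it in its variance. The statistic then varies less than its reference distribution assumes, so the true type I error falls below 0.20 and power is lost.

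Severity is likely to be prognostic here because the stratum is close to the baseline value of the endpoint. Under SAP 4.1 a patient resolves when no counted symptom "has a score higher than 1 over a 72-hour period". By the scoring in Protocol Table 3, a patient with no moderate or severe symptom scores 1 or less on every counted item, and so meets that threshold on entry. The overlap is not exact: a patient whose only moderate symptom is cough falls in the higher stratum but also meets the threshold, because cough is excluded.

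The change is also unexplained. SAP section 1 gives reasons for the shift towards viral load and for leaving out cough, taste and smell, but says nothing about strata. Nor does the revision history.

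**Working it through.** **1. The plan's own design figure.** Inputs from Protocol 8.1: 127 events, HR 1.4, alpha 0.2, two highest doses against placebo (2:1), interim at 73 events, power-family spending with ρ = 2.

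- Interim spend: 0.2 × (73/127)² = 0.0661, so z = 1.506. The bound is exp(1.506/√(73 × 2/9)) = 1.453 (stated 1.45).
- Final alpha with non-binding futility: 0.1862 (stated 0.186). Power: 80.04% (stated 80%).

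The design reproduces, but only with alpha 0.2 taken as one-sided. SAP 6.2 tests at two-sided 0.20, and SAP 6.2.1 removes stopping on efficacy. The matching fixed-design power is Φ(√(127 × 2/9) × ln 1.4 − 1.2816) = Φ(1.788 − 1.282) = 69.4%. That is the baseline for what follows.

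**2. Stratified against unstratified, by simulation.** The inputs on strata are assumptions, because the documents give none. Both runs use 156 patients (104 vs 52), permuted blocks within the four strata, exponential times, within-stratum HR 1.4, and |Z| compared with 1.2816. The Monte Carlo standard error is about 0.6 to 0.8 points.

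- Run A: 20% or 40% with no moderate or severe symptom ("mild" below); 12% over 65 resolving 1.3 times more slowly; 20% of placebo unresolved at Day 28; visits on Days 1–10, 14 and 28.
- Run B: 40% mild; 10% over 65 with no age effect; 20% unresolved overall (156 × 0.8 ≈ 125 events).

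| Mild patients resolve faster by | A: power %, unstratified vs stratified | B: power %, unstratified vs stratified | Type I error, unstratified (A; B) |
|---|---|---|---|
| 1.0 | 69 vs 69 | 66.8 vs 66.3 | not listed; 0.211 |
| 1.5 | 68 vs 69 | 65.6 vs 66.0 | about 0.19; 0.205 |
| 2 | 64–66 vs 67–69 | 63.6 vs 66.8 | 0.18–0.19; 0.180 |
| 3 | 59–63 vs 67 | 58.9 vs 65.7 | 0.15–0.17; 0.165 |

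The stratified test keeps its level: 0.19–0.20 in A and 0.197–0.213 in B. With an age effect of 1.5 added at 2 times, B gives 63.6 vs 67.7%.

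**3. Check on the mechanism.** Under HR 1 with 156 patients, the SD of Z in A was 0.86–0.99 unstratified and 0.99–1.01 stratified. An SD of 0.86 implies a type I error of 2 × [1 − Φ(1.2816/0.86)] = 2 × [1 − Φ(1.490)] = 0.136. This is in line with the 0.140 simulated in the most extreme case below.

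**4. If some mild patients count as resolved at the first visit, in both arms** (run A set-up):

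| Mild | Share of mild resolved at first visit | Power %, unstratified vs stratified |
|---|---|---|
| 15% | half | 63 vs 63 |
| 15% | 80% | 60 vs 62 |
| 30% | 60% | 56.2 vs 58.3 |
| 40% | half | 53 vs 54 |
| 40% | 80% | 42.9 vs 49.5 |

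Most of the fall here comes from the endpoint. Stratifying recovers 0 to 7 points and does not restore 67–70%.

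**5. Single dose against placebo** (52 vs 52, 40% mild): 56–57 vs 59% at 2 times and 51–52 vs 58–59% at 3 times. In the 40%/80% first-visit case it is 37.1 vs 43.4%.

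**The case against.** **The loss may be small.** The larger losses need mild patients to resolve 3 times as fast, and nothing in the documents supports that figure. At 1.5 times the difference is within simulation error or close to it. In the first-visit scenario, which models the threshold argument directly, four of five cases gain about 2 points or less. Meeting the threshold on entry is also not an event: SAP Appendix 1 requires no relapse and a resolved Day 28 assessment. This stands, and is why the size is given as a range.

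**On the one-sided scale of the design, the loss is smaller.** Run B gives 79.3 vs 80.5% at 2 times and 75.8 vs 80.7% at 3 times. The figures are right, but the SAP tests at two-sided 0.20.

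**There is no validity problem.** Type I error is not inflated, and the trial is a proof of concept judged on all its data, with less weight on symptoms. This also stands, and limits the seriousness of the point.

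**The threshold argument belongs to the SAP 4.1 endpoint.** It does not carry over in full to endpoints that require scores of 0, and viral clearance was not simulated. The power figures should not be read across to those endpoints. Stratifying them still follows the randomisation, and cost no meaningful power in the simulations when the strata were not prognostic.

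**The SAP's silence might leave the protocol's strata in force.** This is the weaker reading. The AUC, hospitalisation, oxygen, duration and mortality models in the SAP contain treatment alone, although Protocol 8.3 made stratification the default for regression models. If stratification is intended, the SAP still has to say so.

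**Conclusion.** The concern holds. The departure from the protocol's primary test is certain from the text, unexplained, and not covered by any sensitivity analysis. The direction of the effect is also clear: a conservative test with less power, and no excess of false positives.

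The size depends on assumed prognostic strength and stratum sizes. For the combined comparison at HR 1.4 and two-sided 0.20, the loss is 0 to 1 point at ratios up to 1.5, about 3 points at 2, and 4 to 8 points at 3. Against a fixed-design power of about 69%, the upper part of that range matters for what is still the named primary endpoint. The change should be made, but the trial's overall decision does not turn on it.

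**What to change.** In SAP 6.4.1, restore the two-sided log-rank test stratified by the randomised severity and age factors, for the combined two highest doses and for each dose against placebo. Carry it through 6.4.2.3 and 6.4.3.1 to 6.4.3.3. Keep the unstratified test as a sensitivity analysis. If the sponsor prefers the unstratified test as primary, the SAP should give the reason and add the stratified test as a sensitivity analysis.

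The one drawback is sparse cells. With an assumed 12% over 65 and 40% mild, the over-65 mild cell in a single-dose comparison holds about 104 × 0.12 × 0.40 ≈ 5 patients. The SAP should therefore state that the test pools over age, using severity strata only, when an over-65 cell is sparse. The trigger should be a number applied to blinded counts and fixed before unblinding, so that the choice of primary test is not made on the results. In the run A simulations, four-cell and severity-only stratification differed by no more than 1 point of power in every scenario, so the rule costs essentially nothing.

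The cost is one or two sentences and a STRATA statement. The strata are already recorded for randomisation.
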